**RO7049665—F. Hoffmann-La Roche Ltd**

23/Protocol WP40161, Version 5

**Table 1 Schedule of Activities – Main Table (cont.)**

- a) A 35-day maximum screening period will begin with the first assessment, not from consent.
- b) Participants can be consented up to 3 months prior to randomization.
- c) Randomization may be conducted on Day -1 or Day 1 prior to first dose.
- d) A complete physical examination will be performed at screening (including height and weight), and abbreviated physical examinations at all other visits (no height measurement needed; weight only).
- e) Single measurements of vital signs to be taken before blood collection for laboratory tests but after ECG collection when scheduled at the same time point. Includes single measurements of systolic and diastolic blood pressure, pulse rate, body temperature (tympanic) and respiratory rate. All measurements to be taken after the participant has rested in a supine position for at least 5 minutes. *Vital sign assessments post-dose can be done with a deviation of ± 15 minutes.*
- f) QuantiFERON-TB Gold testing should be performed.
- g) Clinical genotyping is mandatory in countries where permitted.
- h) ECGs should be performed prior to any scheduled vital sign measurements and blood draws. 12-lead ECGs will be obtained in triplicate (three consecutive interpretable 12-lead ECGs within a 2 - 5 minute interval) after the participant has been in a supine position for at least 10 minutes. Automated ECG intervals (PR [PQ], QRS, QT, QTcF) and HR will be captured or calculated, and the changes in T-wave and U-wave morphology will be documented. Measure baseline prior to endoscopy if endoscopy performed on the same day. *ECG assessments post-dose can be done with a deviation of ± 15 minutes.*
- i) Safety tests can be repeated during screening period at discretion of Investigator.
- j) Hepatitis B and HIV 1/2 antibody testing; HCV PCR.
- k) Serum beta-human chorionic gonadotropin (β-HCG) at screening, urine on all other occasions (women of childbearing potential only).
- l) Drugs of abuse screen to include at minimum: amphetamines, barbiturates, cocaine, opiates, and benzodiazepines. Additional testing optional to local standards.
- m) Endoscopy to be performed in the morning prior to dose on Day 29.
- n) *Clostridium difficile* ELISA.

**Table 1 Schedule of Activities – Main Table (cont.)**

- o) Standard breakfast, lunch, dinner and snack to be provided at the times deemed convenient by the site.
- p) For exploratory PD cytokines and other soluble markers.
- q) LRG and ANCA screen. Based on outcome of ANCA screen, p-ANCA, c-ANCA, and atypical p-ANCA may be tested. LRG is optional.
- r) And at additional regular intervals at the Investigator's discretion if an adverse event associated with local tolerability and pain is observed.
- s) Partial Mayo Score.
- t) Site personnel will contact the participant. If deemed required by the Investigator, participants can be asked to come to the site for an unscheduled visit.
- u) IgE, tryptase and exploratory safety biomarkers may be tested in case of participants experiencing signs and symptoms associated with injection-related reactions (IRRs). This includes hypersensitivity reactions.
- v) The Day 50 stool sample for measuring fecal calprotectin can be taken +/- 2 days. The other stool samples should be collected +/- 1 day.
- w) Participants positive for anti-drug antibodies (ADA) will be requested to return and have additional ADA and sCD25 samples to monitor off-treatment ADA persistence.
- x) *Safety laboratory assessments on Day 50 are only for participants enrolled in dose level 3 (15 mg, Q2W).*
- y) *PK samples collected within 24 hours post-dose, can be taken with a deviation of  $\pm$  15 minutes for samples taken up to 6 hours after dosing with RO7049665/ placebo, and for samples thereafter with a deviation of  $\pm$  30 minutes.*

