## **7.1 DISCONTINUATION OF STUDY TREATMENT**

Dosing will be stopped in a given individual as described in [Section 4.1.4](#).

Participants who discontinue study treatment prematurely will be asked to return to the clinic for a study completion/early termination visit (see [Section 8.10.3](#)) and may undergo follow-up assessments (see [Section 8.10.4](#)). See the SoA ([Section 1.3](#)) for data to be collected at the time of treatment discontinuation and follow-up and for any further evaluations that need to be completed.

The primary reason for premature study treatment discontinuation should be documented on the appropriate eCRF.

Reasons for discontinuation of study treatment (or withdrawal from the study) include, but are not limited to, the following:

- Participant withdrawal of consent at any time.
- Any medical condition that the Investigator or Sponsor determines may jeopardize the participant's safety if he or she continues in the study.
- Investigator or Sponsor determination that treatment discontinuation is in the best interest of the participant.
- Pregnancy.

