### **8.3.1 Time Period and Frequency for Collecting Adverse Event and Serious Adverse Event Information**

The method of recording, evaluating, and assessing causality of AEs and SAEs and the procedures for completing and transmitting SAE reports are provided in [Appendix 2](#).

Investigators will seek information on adverse events at each participant's contact. All AEs, whether reported by the participant or noted by study personnel, will be recorded in the participant's medical record and on the Adverse Event eCRF as follows:

**After informed consent** has been obtained **but prior to initiation of study treatment**, only SAEs caused by a protocol-mandated intervention should be reported (e.g., SAEs related to invasive procedures such as biopsies). Any other adverse event should not be reported.

**After initiation of study treatment**, all AEs, regardless of relationship to study treatment, will be reported until the Day 99 safety and follow-up visit, or, 28 days after the last dose of study treatment in case of early termination.

**Post-study adverse events and serious adverse events:** The Investigator is not required to actively monitor participants for AEs after the final follow-up visit.

However, if the Investigator learns of any SAE (including a death) or other AEs of concern that are believed to be related to prior treatment with study treatment, at any time after a participant has been discharged from the study, and the Investigator considers the event to be reasonably related to the study treatment or study participation, the Investigator must promptly notify the Sponsor. For the procedure of reporting, see [Appendix 2](#).

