### **Blood samples**

Blood samples will be collected for the following assessments:

- To quantify relative and absolute WBC counts (T cells, B cells, NK cells, and eosinophils) by flow cytometry as well as complete white blood count differential. Tests include (but are not limited to) markers for quantification and characterization of  $T_{reg}$ s and  $T_{eff}$  cell subsets CD3, CD4, CD8, CD25, CD127 and FoxP3.
- Additional blood samples will be collected for potential evaluation of T cell subset specific methylation signature changes induced by drug. Decision to perform this exploratory assessment involving deoxyribonucleic acid (DNA) extraction will be made based on emerging PD data.

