### **8.10.3 Assessments at Study Completion/Early Termination Visit**

Participants who complete the study (defined in Section 4.4) will be asked to return to the clinic 56 days after the last dose of study drug for a follow-up visit.

Participants who discontinue from the study early will be asked to return to the clinic 28 days after the last dose of study drug for a follow-up visit.

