### 9.3.2 Safety Analyses

All safety analyses will be based on the Safety analysis population, with participants grouped according to the treatment received (dose level / dose frequency).

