**Table 7 Safety Statistical Analysis Methods**

Endpoint	Statistical Analysis Methods
Adverse events	The original terms recorded on the eCRF by the Investigator for adverse events will be coded by the Sponsor. Adverse events will be summarized by mapped term and appropriate thesaurus level.
Clinical laboratory tests	All clinical laboratory data will be stored on the database in the units in which they were reported. Laboratory test values will be presented in International System of Units (SI units; Système International d'Unités) by individual listings with flagging of abnormal results. Summary tables of change from baseline over time will be displayed. See Appendix 4 for details on standard reference ranges and data transformation and the definition of laboratory abnormalities.
Vital signs	Vital signs data will be presented by individual listings with flagging of values outside the normal ranges and flagging of abnormalities. In addition, tabular summaries will be used, as appropriate.
ECG data analysis	ECG data will be presented by individual listings. In addition, tabular summaries will be used, as appropriate.
Concomitant medications	The original terms recorded on the participants' eCRF by the Investigator for concomitant medications will be standardized by the Sponsor by assigning preferred terms. Concomitant medications will be presented in summary tables and listings.
Other	Physical examination results, safety biomarkers and incidence of ADAs will be listed and summarized descriptively.

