## **Additional Statistical Considerations for Clinical Laboratory Data**

- **Standard Reference Ranges and Transformation of Data**

Roche standard reference ranges, rather than the reference ranges of the Investigator, will be used for all parameters. For most parameters, the measured laboratory test result will be assessed directly using the Roche standard reference range. Certain laboratory parameters will be transformed to Roche's standard reference ranges.

A transformation will be performed on certain laboratory tests that lack sufficiently common procedures and have a wide range of Investigator ranges, e.g., enzyme tests that include AST, ALT, and alkaline phosphatase and total bilirubin. Since the standard reference ranges for these parameters have a lower limit of zero, only the upper limits of the ranges will be used in transforming the data.

- **Definition of Laboratory Abnormalities**

For all laboratory parameters included, there exists a Roche predefined standard reference range. Laboratory values falling outside this standard reference range will be labeled "H" for high or "L" for low in participant listings of laboratory data.

In addition to the standard reference range, a marked reference range has been predefined by Roche for each laboratory parameter. The marked reference range is broader than the standard reference range. Values falling outside the marked reference range that also represent a defined change from baseline will be considered marked laboratory abnormalities (i.e., potentially clinically relevant). If a baseline value is not available for a participant, the midpoint of the standard reference range will be used as the participant's baseline value for the purposes of determining marked laboratory abnormalities. Marked laboratory abnormalities will be labeled in the participant listings as "HH" for very high or "LL" for very low.

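### Do the extra Day 50 laboratory tests at 15 mg, and the shorter adverse event window after early termination, distort the safety comparison across doses?

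*Combined protocol and SAP*

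**What the plan says.** Footnote x to Table 1 in Section 1.3 limits one laboratory visit to the top dose: "Safety laboratory assessments on Day 50 are only for participants enrolled in dose level 3 (15 mg, Q2W"). The rationale for Version 5 gives the purpose: added monitoring at 15 mg, with eosinophils followed alongside flow cytometry.

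For adverse events, Section 8.3.1 runs collection "until the Day 99 safety and follow-up visit, or, 28 days after the last dose of study treatment in case of early termination". Section 8.10.3 matches it: "Participants who discontinue from the study early will be asked to return to the clinic 28 days after the last dose of study drug". Section 7.1 covers those who stop treatment: "Participants who discontinue study treatment prematurely will be asked to return to the clinic for a study completion/early termination visit". It adds that they may have follow-up assessments.

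Table 4 makes the incidence of adverse events and of abnormal laboratory findings primary endpoints. On analysis, Section 9.3.2 says: "All safety analyses will be based on the Safety analysis population, with participants grouped according to the treatment received". For laboratory data, Table 7 asks for listings with abnormal results flagged, and "Summary tables of change from baseline over time will be displayed". Appendix 4 defines abnormality value by value: "Values falling outside the marked reference range that also represent a defined change from baseline will be considered marked laboratory abnormalities". None of these sections names a common visit set, a follow-up cut-off or a person-time denominator. Section 9.1 states no hypothesis.

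**The concern.** The chance that a participant ever shows an abnormal value rises with the number of times the value is measured. If the laboratory endpoint is read as the share of participants with any abnormal post-dose value, 15 mg gets one more opportunity than the lower doses and could look worse with no true dose effect. Placebo pooled over dose levels would mix participants with 10 and 11 draws. Day 50 falls one week after the fourth dose, and eosinophilia is one of the commonest adverse events reported so far, so the extra draw comes at a sensitive time.

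The adverse event window raises a similar worry in the other direction. Someone who leaves early is observed for a shorter time after the last dose, so an arm with more early terminations could show fewer late-onset events. At stake is the comparison of primary safety endpoints across doses.

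**Working it through.** **The plan's own figures.** Section 9.2 gives the chance of seeing at least one adverse event of true incidence 20%. With 8 participants, 1 − 0.8^8 = 83.2% (stated 83%). With 4, 1 − 0.8^4 = 59.0% (stated 59%). Both reproduce.

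**Number of draws.** The hematology row of Table 1 has six marks after Day −1 up to Day 36, then Days 43, 57, 71 and 99 for everyone: 6 + 4 = 10. Day 50 makes 11 at dose level 3. The columns of the first part do not line up in the text available, so the count is firm but the exact days are not.

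**Size of the laboratory effect.** The documents give no per-draw risks, so 5, 10 and 20% are assumptions. With independent draws, the share ever abnormal is 1 − (1 − p)^k. The correlated case is beta-binomial with an assumed within-person correlation of 0.3.

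| Risk per draw | Independent, 10 draws | Independent, 11 draws | Gap (points) | Gap at correlation 0.3 (points) |
|---|---|---|---|---|
| 5% | 40.1% | 43.1% | 3.0 | 0.8 |
| 10% | 65.1% | 68.6% | 3.5 | 1.2 |
| 20% | 89.3% | 91.4% | 2.1 | 1.5 |

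One participant in eight is 100/8 = 12.5 points. The gaps are therefore between 0.8/12.5 = 0.06 and 3.5/12.5 = 0.28 of a participant.

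**Least favourable case.** Suppose abnormalities arise only one week after a dose, at 3 draws against 4. The gaps are then 14.3 against 18.5% (4.3 points), 27.1 against 34.4% (7.3) and 48.8 against 59.0% (10.2), at most 10.2/12.5 = 0.82 of a participant.

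**Adverse event window.** Completers are followed for 99 − 43 = 56 days after the last dose. Assume a constant hazard giving 40% over the 98 days from Day 1 to Day 99, so incidence over w days is 1 − 0.60^(w/98).

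| Last dose received | Followed 28 days after it | Followed 56 days after it | Loss per stopper (points) | Loss per arm, one stopper in 8 (points) |
|---|---|---|---|---|
| 1 | 28 days: 13.6% | 56 days: 25.3% | 11.7 | 1.5 |
| 2 | 42 days: 19.7% | 70 days: 30.6% | 10.9 | 1.4 |
| 3 | 56 days: 25.3% | 84 days: 35.5% | 10.1 | 1.3 |

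For drug-related events these figures are more likely too large than too small, because Section 2.2.2.1 expects near-complete washout within two weeks of the last dose.

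**Which outputs are touched.** Change-from-baseline tables by visit are not altered by an extra visit; Day 50 simply appears as a time point for dose level 3. Footnote x covers everyone enrolled at that level, so 15 mg and its concurrent placebo have equal draws. The stopping rules in Section 4.1.3 count participants within one dose level, and 15 mg is the highest level planned, so no stated escalation rule rests on the affected comparison.

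**The case for a change.** The strongest case for a change is that Table 4 uses the word incidence for a primary endpoint and Section 9 never says how it is computed. A participant at 7.5 mg with a transient abnormality on Day 50 would have no scheduled safety-laboratory draw to catch it. With about two placebo participants per cohort, pooling placebo over dose levels is likely. Early stopping could plausibly depend on arm, since the criteria in Section 4.1.4 include related severe events and disease exacerbation. Settling the tables before database closure would cost only wording.

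The facts in this case stand, and so does the silence on how incidence is computed. Their weight is small:

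- The any-visit table compared across doses is inferred; Table 7 does not ask for it. An analyst who builds one will see that Day 50 exists at only one level, and can restrict the comparison to shared visits or annotate it from the flagged listings.
- The 10.2-point case needs zero risk at every other draw, independence, and exactly three one-week draws at the lower doses, which the table as read does not settle. Eosinophils, the natural candidate for it, also have a second source. Section 8.6 has blood taken "To quantify relative and absolute WBC counts (T cells, B cells, NK cells, and eosinophils) by flow cytometry", and that sampling is scheduled on Day 50 at all dose levels.
- The 28-day rule is identical in every arm. An event that caused the stop is already counted, and related serious events and related events of concern that the investigator learns of later must still be reported.
- Exposure-adjusted rates would not be a clean gain. They suit a roughly constant hazard. An event tied to the first dose counts as 1 per 28 days in someone who stops after that dose but 1 per 98 days in a completer, a 3.5-fold artefact (98/28) where crude incidence has none.

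**Conclusion.** No change to the plan is needed. The Day 50 draw is a deliberate, disclosed safety measure that leans towards finding harm at the highest dose. Its effect on a cross-dose any-visit table would be about 1 to 4 points under the assumed per-draw risks, less than a third of one participant at eight per group; even the least favourable case stays below one participant. The adverse event window moves an arm by 1.3 to 1.5 points per stopper in eight, and biases a comparison only if early termination differs between arms.

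What remains is missing detail in table specification, which analysts can supply from data and listings already planned. All the sizes rest on assumed rates, an assumed correlation and a constant hazard, because the documents give no per-visit frequencies. The conclusion would weaken if the study report leaned on an any-visit laboratory incidence compared across doses without noting the unequal schedule, or if early terminations proved clearly unbalanced by arm.

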**Table 2 Schedule of Activities - Detailed Table**

Visit	Day	Scheduled Time (h)	Vital Signs b	Physical Examination c	ECG-12 lead d	PK Sample e	ADA	Blood Flow Cytometry	Blood Epigenetic Testing	sCD25	Local Pain and Skin Reactivity
Dose 1 in-house period a	Day -1		x	x			x	x			
	Predose		x		x	x		x	x	x	
	0										
	2		x								
	6			x		x					
	12				x	x					x
Dose 1 outpatient visits	Day 24		x	x	x	x		x		x	
	Day 4					x					
	Day 6					x		x	x	x	
	Day 8					x	x	x	x	x	
Dose 2 in-house period	Day 10					x		x	x		
	Predose		x	x	x	x	x	x	x	x	
	0										
	12				x						x
Dose 2 outpatient visit	Day 15		x								
Dose 3 in-house period	Day 16										
	Day 22					x	x	x			
	Predose		x	x	x	x	x	x		x	
	0										
Dose 3 outpatient visit	Day 29		x								
	Day 12										x
	Day 30		x								
	Day 36					x		x			
Dose 4 in-house period	Predose		x	x	x	x	x	x	x	x	
	0										
	Day 43		x								
	2										
	6				x						
Dose 4 outpatient visits	12				x	x					x
	Day 44	24	x		x	x				x	
	Day 46					x					
	Day 48					x		x	x	x	
	Day 50					x		x	x	x	
	Day 52					x		x	x	x	
Follow Up visit	Day 57					x	x	x	x		
	Day 71					x	x	x	x	x	
Unscheduled visit	Anytime		x	x	x	x	x	x	x	x	x
Hypersensitivity/ IRR (≥ Grade 2)	Anytime		x	x		x	x				x
Early Termination Visit	Anytime		x		x	x	x				x

RO7049665—F. Hoffmann-La Roche Ltd

26/Protocol WP40161, Version 5

**Table 2 - Schedule of Activities - Detailed Table – (cont.)**

- a) Randomization may be conducted on D-1 or D1 prior to first dose.
- b) Single measurements of vital signs to be taken before blood collection for laboratory tests but after ECG collection when scheduled at the same time point. Includes single measurements of systolic and diastolic blood pressure, pulse rate, body temperature (tympanic) and respiratory rate. All measurements to be taken after the participant has rested in a supine position for at least 5 minutes. *Post-dose vital sign assessments can be done with a deviation of  $\pm 15$  minutes.*
- c) A complete physical examination will be performed at screening (including height and weight), and abbreviated physical examinations at all other visits (no height measurement needed; weight only).
- d) ECGs should be performed prior to any scheduled vital sign measurements and blood draws. 12-lead ECGs will be obtained in triplicate (three consecutive interpretable 12-lead ECGs within a 2-5 minute interval) after the participant has been in a supine position for at least 10 minutes. Automated ECG intervals (PR [PQ], QRS, QT, QTcF) and HR will be captured or calculated, and the changes in T-wave and U-wave morphology will be documented. Measure baseline prior to endoscopy if endoscopy performed on the same day. *Post-dose ECG assessments can be done with a deviation of  $\pm 15$  minutes.*
- e) *PK samples collected within 24 hours post-dose can be taken with a deviation of  $\pm 15$  minutes for samples taken up to 6 hours after dosing with RO7049665/ placebo, and for samples thereafter with a deviation of  $\pm 30$  minutes.*

## **2. INTRODUCTION**

### **2.1 STUDY RATIONALE**

RO7049665 is a novel dimeric interleukin 2 (IL-2) mutein that is being developed as a therapy for autoimmune conditions, including ulcerative colitis (UC). It is expected to treat the impaired regulatory T cell ( $T_{reg}$ ) numbers or function associated with autoimmune diseases without the broad-based immunostimulatory effects of IL-2. Specifically, RO7049665 was engineered to address and overcome the pharmacologic, safety and functional liabilities of Proleukin® (aldesleukin), a recombinant human IL-2 therapy currently approved for the treatment of renal cell carcinoma and malignant melanoma.

Study (WP40161) has taken into consideration experiences gained in the healthy volunteer entry-in-human (EIH) single ascending dose (SAD) study WP39826. This is the first study where RO7049665 is administered in multiple doses and to participants with an autoimmune condition. The primary objective of this study is to evaluate the safety and tolerability of RO7049665 in participants with active UC. In addition, secondary objectives to be assessed are the pharmacokinetics (PK), preliminary efficacy, pharmacodynamics (PD) and immunogenicity. The study results will be used to support further clinical development of RO7049665.

The rationale for the study design is provided in Section [4.2](#).

